7.3 Follow-up of Adverse Events

All adverse events will be followed with appropriate medical management until resolved. Patients removed from study for unacceptable adverse events will be followed until resolution or stabilization of the adverse event. For selected adverse events for which administration of the investigational drug was stopped, a re-challenge of the subject with the investigational drug may be conducted if considered both safe and ethical by the Investigator.

7.4 Expedited Reporting

7.4.1 Reporting to the HDFCCC Data and Safety Monitoring Committee

If a death occurs during the treatment phase of the study or within 30 days after the last administration of the study drug(s) and it is determined to be related either to the study drug(s) or to a study procedure, the UCSF PI or his/her designee must notify the DSMC Chair (or qualified alternate) within 1 business day of knowledge of the event. The contact may be by phone or e-mail.

7.4.2 Reporting to Institutional Review Board

The Principal Investigator must report events meeting the UCSF CHR definition of “Unanticipated Problem” (UP) and the San Francisco VA Medical Center within 5 business days of his/her awareness of the event.

7.4.3 Expedited Reporting to the FDA

If the study is being conducted under an IND, the Sponsor (or the Sponsor-Investigator) is responsible for determining whether or not the suspected adverse reaction meets the criteria for expedited reporting in accordance with federal regulations (21 CFR §312.32).

The Sponsor (or Sponsor-Investigator) must report in an IND safety report any suspected adverse reaction that is both serious and unexpected. The Sponsor needs to ensure that the event meets all three definitions:

- Suspected adverse reaction (as defined in 7.1.4)
- Unexpected (as defined in 7.1.5)
- Serious (as defined in 7.1.6)

If the adverse event does not meet all three of the definitions, it should not be submitted as an expedited IND safety report.

The timeline for submitting an IND safety report to FDA is no later than **15 calendar days** after the Investigator determines that the suspected adverse reaction qualifies for reporting (21 CFR 312.32(c)(1)).

Any unexpected fatal or life-threatening suspected adverse reaction will be reported to FDA no later than **7 calendar days** after the Investigator’s initial receipt of the information (21 CFR 312.32(c)(2)).

Any relevant additional information that pertains to a previously submitted IND safety report will be submitted to FDA as a Follow-up IND Safety Report without delay, as soon as the information is available (21 CFR 312.32(d)(2)).

Please see Appendix 2 for further details on the UCSF Helen Diller Family Comprehensive Cancer Center (HDFCCC) Data and Safety Monitoring Committee (DSMC) policies and procedures.

8 Evaluation of Efficacy

8.1 Determination of Positive or Negative Disease Status

8.1.1 FET PET Blinded Reads

All imaging studies will be reviewed by three nuclear medicine physicians blinded to the patient's history and their pathology. Each physician will undergo a reader-training course that will involve FET PET cases not included in the study reads. Image interpretation will involve 1) qualitative, 2) quantitative, and 3) overall assessments.

1) Qualitative/Visual Assessment

For each lesion, readers will assess whether increased tracer uptake is consistent with progression/recurrence (positive) or TRC (negative).

2) Quantitative Assessment

Quantitative assessments will be performed on transaxial slices showing the highest FET accumulation, as described by Galldiks (6). The SUVmax, TBRmax and TBRmean and size information will be collected. Based on the quantitative assessments, readers will evaluate in a binary fashion for progression/recurrence (positive) or TRC (negative) as defined in Galldiks (6) (TBRmax ≥ 2.3 and/or TBRmean ≥ 2.0 for use in indeterminate cases).

3) Overall Assessment

Based on qualitative and quantitative assessments, readers will make an overall determination whether FET uptake is most consistent with progression/recurrence (positive) or TRC (negative). In cases where readers disagree with the quantitative assessment, based on their expert judgement, they will be prompted to provide comments. The overall assessment will be the positive or negative determination for FET PET.

8.1.2 Standard of Truth

8.1.2.1 Composite Standard of Truth

A composite standard of truth (CSOT) for recurrence or TRC will be evaluated by a panel of physicians (Truth Panel) independent of the FET images, FET imaging reports, or FET blinded reads. The CSOT will be determined based on histopathology reports and other available clinical information, including prior imaging, subsequent imaging, tumor board notes, clinical notes. Histopathology of the target lesion obtained (biopsy, resection) within three months after the PET imaging session will be reviewed (although the Truth Panel will have access for up to six months after the PET imaging session). There is no agreed upon cutoff for determining recurrent tumor in the setting of gliomas. A 20% cutoff is often used, but a truth panel will include a pathologist for manual re-review of histopathology. Positive for recurrence on follow-up imaging will be based on RANO 2.0 criteria (4).

For lesion-level reference standard, features of RANO will be leveraged as part of the overall assessment and will be considered in evaluating lesion-level results. Histopathology and imaging will be the primary factors used in the determination, followed by additional clinical data available as part of tumor board notes. From this data, an overall determination will be made for each individual lesion, and this will be considered together with the patient-level determination (as per RANO).

In patients where the histopathology and RANO determination are concordant, the patient will be characterized based on the concordant results. If the patient does not have subsequent imaging available (either the patient declined clinically or the lesion was resected and so not present on subsequent imaging), the patient will be characterized based on histopathology for lesions resected or as progressive disease if there is clinical decline or death.

There will be many complicating factors for the CSOT:

1. The use of steroids and bevacizumab can impact lesion enhancement independent of actual progression. For example, a lesion may have decreased enhancement after a patient starts bevacizumab, but in fact have progressive disease (pseudo- response). In this case the RANO determination would be PR, while the patient could be characterized as recurrent disease by the Truth Panel. In order to take this into consideration, the Truth Panel will look at subsequent imaging studies to determine the appropriate characterization.
2. The goal of this study is to characterize existing lesions on the FET PET. If new lesions develop on follow-up imaging that are not in the same location or related to the original lesion of concern at time of FET PET, this will not be characterized as recurrent disease. This same issue may exist with histopathology, where a new lesion geographically distinct from the baseline lesion may be sampled and positive for tumor, but the lesion of concern was unchanged and not biopsied. The Truth Panel will take this into account when determining the characterization of the lesion.
3. Patients without imaging or histopathology due to clinical progression (hospice and/or death) will be characterized as recurrent disease.

The CSOT of progression/recurrence (positive) or TRC (negative) will be determined for each individual lesion and for each subject overall.

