2.3 Exploratory Objectives

| Exploratory Objectives |
|---|
| 1. To assess relationships between serial FET PET and clinical outcome (benign TRC and recurrence) in patients with recurrent metastatic lesions, recurrent high grade gliomas and recurrent low grade gliomas. |
| 2. To determine if MRI can differentiate between benign treatment- related changes and recurrence. |
| 3. To describe the distribution of the standardized uptake value (SUV) and tumor-to-background ratio (TBR) for observed lesions. |
| 4. To determine if FET PET can differentiate between benign TRC and recurrent metastatic lesions. |
| 5. To determine if FET PET can accurately differentiate between low-grade and high-grade gliomas in population 2. |

3 Study Design

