9.2.3 Analysis of Secondary Endpoints

For the secondary endpoints for performance characteristics, both the composite reference standard and histopathology alone will be used in separate calculations. Only the efficacy analysis set will be analyzed for secondary efficacy endpoints; the per protocol population will not be analyzed. TP, FP, FN, and TN are defined as described in [Section 8.1.3](#).

Calculations will be done to determine the subject-specific and lesion-specific sensitivity, specificity, positive predictive value, negative predictive value, accuracy, and misclassification rate for FET PET. These analyses will use the blinded readers' overall assessment, not the visual/qualitative or quantitative assessments.

For the secondary analyses of sensitivity, specificity, PPV, NPV, accuracy, and misclassification rate that use histopathology as the standard of truth, analysis will be performed only on subjects who have known histopathology status. No imputation will be made for these endpoints.

Inter-reader variability will be analyzed using Fleiss' kappa statistic to determine the agreement between three independent blinded readers in assessing FET PET images as recurrence or TRC. Separate analyses of inter-reader variability will be done for the readers' qualitative/visual assessments, quantitative assessments, and overall assessments.

Intra-reader variability will be analyzed based on a random sample of 15 subjects whose images were re-reviewed by the same reader. The percent of agreement between the two interpretations will be computed for each reader. Cohen's kappa statistics will be used to determine the reproducibility of the assessment by individual readers when analyzing the same data repeatedly. Separate analyses of intra-reader variability will be done for the reader's qualitative/visual assessments, quantitative assessments, and overall assessments.

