9.2.4 Exploratory Analysis

Exploratory analysis will be performed on patients with glioma who are under suspicion for progression or recurrence. For these participants, standard-of-care MRI performed during the FET PET/MRI will undergo retrospective analysis by a panel of three blinded independent neuroradiologists. The neuroradiologists will classify the findings as positive (indicating recurrence) or negative (indicating TRC) and compare them with the CSOT. The 3 readers will be blind to 18F-FET PET images, prior imaging results, clinical data, surgical reports, and histopathological results.

SUV and TBR results (SUVmean, SUVmax, SUVpeak, TBRmean, and TBRmax) will be summarized by descriptive statistics for each reader on a lesion-specific basis.

Exploratory analysis will also be performed to assess relationships between serial FET PET and clinical outcome (benign TRC and recurrence) in patients with recurrent metastatic lesion, recurrent high-grade gliomas and recurrent low-grade gliomas (Population 1).

Exploratory analyses will also be performed to determine if FET PET can differentiate between benign TRC and recurrent metastatic lesions and to determine if FET PET can accurately differentiate between low-grade and high-grade gliomas in population 2.

10 Study Management

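### Exploratory objective 2 scores the MRI reads only against a composite truth that itself uses imaging and does not withhold MRI, so MRI accuracy is at risk of upward bias of unknown size; a histopathology table would address this cheaply

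*Combined protocol and SAP*

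**What the plan says.** Exploratory objective 2 (section 2.3) reads "To determine if MRI can differentiate between benign treatment- related changes and recurrence". Section 9.2.4 implements it in glioma patients with suspected progression or recurrence: "standard-of-care MRI performed during the FET PET/MRI will undergo retrospective analysis by a panel of three blinded independent neuroradiologists". Then: "The neuroradiologists will classify the findings as positive (indicating recurrence) or negative (indicating TRC) and compare them with the CSOT". No other reference standard is named for MRI. The MRI readers are masked: "The 3 readers will be blind to 18F-FET PET images, prior imaging results, clinical data, surgical reports, and histopathological results".

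Section 8.1.2.1 defines the CSOT. "The CSOT will be determined based on histopathology reports and other available clinical information, including prior imaging, subsequent imaging", and the list goes on to notes from the tumor board and the clinic. For lesions, tissue and imaging carry the most weight. A positive call on follow-up imaging follows RANO 2.0. The Truth Panel works "independent of the FET images, FET imaging reports, or FET blinded reads". No matching restriction covers MRI. Clinical decline, hospice or death can also settle the label when imaging or tissue is missing.

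For FET, section 9.2.3 states that "both the composite reference standard and histopathology alone will be used in separate calculations". Section 8.1.2.2 already has the panel make a histopathology call wherever tissue exists, as an intermediate step of its overall review.

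**The concern.** A test scored against a standard that draws on the same test tends to look better than it is. If a misleading MRI appearance sways both the blinded reader and the panel, the shared error is counted as a correct MRI read. A FET read that was right in that patient is counted as wrong.

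FET has a second, histopathology-only analysis in which this mechanism is weaker. MRI has none. The answer to exploratory objective 2 therefore rests wholly on the standard in which MRI takes part. MRI and FET figures reported on one CSOT also invite a side-by-side reading, although the plan does not test that contrast.

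**Working it through.** **1. The sections side by side.** The scan scored in 9.2.4 is one specific MRI, acquired with the FET PET. The panel's list in 8.1.2.1 covers earlier and later imaging and neither names nor excludes that scan. The same section ties the truth call to the lesion as it stood when FET PET was done, and 6.1.2 looks for change in size on imaging within six months of FET PET. Judging change needs a baseline, so use of the session MRI is likely but not stated. If it were withheld, later MRI could still share its failure modes: section 1.2 says enhancement is an unreliable marker of tumor after treatment.

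Section 8.1.2.1 gives a rule for concordant tissue and RANO results but no explicit rule for discordant ones, so imaging may also influence some labels in patients with tissue.

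**2. Inputs for an illustration.**
- MRI 0.82/0.76 (sensitivity/specificity), from the superseded high-grade sizing in 9.1.2. That section's MRI misclassification rate reproduces: 0.70 × 0.18 + 0.30 × 0.24 = 0.198.
- FET 0.81/0.79 and prevalence p = 0.50, from 9.1.1.
- Share without tissue u = 0.60, from the 40% with pathology in 9.1.2; u = 0.40 is shown as an alternative.
- f, the share mislabelled among no-tissue patients in whom MRI misleads, is an assumption. The documents give no basis for estimating it.
- MRI and FET errors are taken as independent given the truth.

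**3. Mislabelling that follows MRI.** Let a = u·f·p·(1 − Se_MRI) be recurrences labelled TRC, and b = u·f·(1 − p)·(1 − Sp_MRI) be TRC labelled recurrence. Labelled positives are P = p − a + b; labelled negatives are N = 1 − P.

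- MRI: Se' = (p·Se_MRI + b)/P; Sp' = ((1 − p)·Sp_MRI + a)/N
- FET: Se' = (Se_FET·(p − a) + (1 − Sp_FET)·b)/P; Sp' = (Sp_FET·(1 − p − b) + (1 − Se_FET)·a)/N

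For u = 0.60 and f = 0.25: a = 0.0135, b = 0.018, P = 0.5045, N = 0.4955. MRI Se' = 0.428/0.5045 = 0.848 and Sp' = 0.3935/0.4955 = 0.794. FET Se' = 0.3978/0.5045 = 0.789 and Sp' = 0.3833/0.4955 = 0.774.

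| u | f | MRI | FET | Specificity, FET − MRI |
|---|---|---|---|---|
| any | 0 | 0.82/0.76 | 0.81/0.79 | +0.03 |
| 0.60 | 0.10 | 0.83/0.77 | 0.80/0.78 | +0.01 |
| 0.60 | 0.25 | 0.85/0.79 | 0.79/0.77 | −0.02 |
| 0.60 | 0.50 | 0.88/0.83 | 0.77/0.76 | −0.07 |
| 0.40 | 0.25 | 0.84/0.78 | 0.80/0.78 | about 0 |

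**4. Leakage in either direction.** Section 5.2.1.1 has FET formally reported, passed to the neurosurgeon and available for planning biopsy and surgery. The panel then receives tumor board and clinical notes, and no redaction step is described. Take a second model in which a share 0.2 of all labels simply copies one test and the rest are true (p = 0.50). Both tests are positive in 0.5 × 0.82 × 0.81 + 0.5 × 0.24 × 0.21 = 0.3573 of patients, and both negative in 0.5 × 0.18 × 0.19 + 0.5 × 0.76 × 0.79 = 0.3173.

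- Labels copy MRI (P = 0.8 × 0.5 + 0.2 × 0.53 = 0.506): MRI reads 0.858/0.806 and FET 0.782/0.768. Specificity difference: 0.768 − 0.806 = −0.038.
- Labels copy FET (P = 0.8 × 0.5 + 0.2 × 0.51 = 0.502): FET reads 0.849/0.831. MRI reads (0.8 × 0.41 + 0.2 × 0.3573)/0.502 = 0.796 and (0.8 × 0.38 + 0.2 × 0.3173)/0.498 = 0.738. Specificity difference: 0.831 − 0.738 = +0.093.

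The true difference is +0.03. The contrast moves down in one case and up in the other.

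**The case against.** The strongest reply has four parts.

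- **The blinded MRI reads are not an input to the panel.** The panel judges change over time with tissue, RANO, notes and clinical course, and 8.1.2.1 tells it to look past a misleading drop in enhancement by using later scans. Follow-up can overturn a misleading baseline appearance. This stands, and it means that inflation is a risk and has not been shown.
- **The illustration has its direction built in.** The first model assigns every panel error to patients in whom MRI misled. The 60% without tissue comes from superseded high-grade sizing with a four-week pathology window, whereas the CSOT reviews tissue within three months and has access up to six. The MRI figures come from one cited study. All of this stands.
- **Nothing planned turns on it.** Objective 2 has no threshold, no FET-versus-MRI test is planned, and study success uses fixed limits for FET alone. With 118 × 0.50 = 59 negatives, the unpaired 95% half-width for a specificity difference is 1.96 × √(0.76 × 0.24/59 + 0.79 × 0.21/59) = 0.15, wider than the whole modelled shift of about 0.10 (+0.03 to −0.07). This stands and sets the priority.
- **Tissue is not neutral either.** FET can guide sampling, so a histopathology subset may favor FET. This stands and must be disclosed.

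A reader might infer that FET gets no comparable help because the panel is kept from it. The documents do not support that: the bar covers FET images, reports and blinded reads, while notes written after clinicians received the FET findings still reach the panel.

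None of these replies supplies the missing item: MRI has no analysis against a standard that leaves imaging out.

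**Conclusion.** The point holds as a risk. MRI reads are scored only against a CSOT in which imaging is a leading component and from which MRI is not withheld, while FET also has a histopathology-only analysis. The likely effect on MRI taken alone is upward. Under the assumed values in the first model it ranges from about 0.01 (f = 0.10) to 0.06–0.07 (f = 0.50), but f is assumed and the no-tissue share is borrowed from superseded sizing, so these figures are illustrations and not estimates.

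Two stronger readings are tempting. One is that the MRI under test is part of its own reference standard and its accuracy is therefore inflated. The text does not say that the panel sees the session MRI, and truth without tissue also uses clinical decline, hospice or death. The other is that the CSOT favors MRI over FET and reverses their ranking. With possible leakage on both sides, the net direction is unknown.

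This is a cheap improvement of low priority. It concerns an exploratory objective, and no study decision depends on it.

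**What to change.** In section 9.2.4:

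- Add a table of the blinded MRI reads against the histopathology standard of truth (8.1.2.2) in glioma patients with tissue, with the FET reads in the same patients beside it. This parallels the histopathology analysis that 9.2.3 already plans for FET.
- Keep MRI versus CSOT, labelled as a comparison with a standard that uses MRI, and do not use it as a benchmark for FET.

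In section 8.1.2:

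- Have the panel record its histopathology call before it reviews imaging.
- State whether the panel sees the session MRI.

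The cost is one table, some wording and a small change to the order of panel review; no new patient data are needed. The downsides to disclose are fewer patients, wider intervals, and a tissue-selected subset whose sampling FET may have guided. On the superseded 40% figure, 0.40 × 118 is about 47 patients. With about 24 of them negative, the 95% half-width around a specificity of 0.76 is 1.96 × √(0.76 × 0.24/24) = 0.17, against 0.11 with 59 negatives. The longer tissue window in 8.1.2.1 may raise that number. Restriction to patients scanned on PET/MRI may lower it.

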8.1.2.2 Histopathology Standard of Truth

For cases with available histopathology, the histopathology standard of truth for recurrence (positive) or TRC (negative) will also be determined by the Truth Panel as an intermediate result while reviewing histopathology as part of their overall assessment of each lesion and each subject.

8.1.3 Comparison of FET PET to Standard of Truth

The results of the FET PET scan will be compared to a standard of truth (either CSOT or histopathology standard of truth, as described above).

8.1.3.1 Lesion-level Analyses

For lesion-specific analyses, lesions will be classified as either TP, FP, TN, or FN:

- True positive (TP): FET PET read as positive for progression/recurrence, standard of truth confirms tumor progression/recurrence.
- False positive (FP): FET PET read as positive for progression/recurrence, standard of truth does not confirm progression/recurrence.
- True negative (TN): FET PET read as negative for progression/recurrence, standard of truth confirms negative for progression/recurrence.

- False negative (FN): FET PET read as negative for progression/recurrence, standard of truth does not confirm progression/recurrence.
- For any lesion that is recorded by only one of the expected evaluations (either by a blinded reader or by the standard of truth) after receiving both evaluations, the non-recorded evaluation will be assessed as negative for determination of the lesion-specific result (TP, FP, TN, or FN).

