9.1.2 Initial Sample Size Calculation

Prior to protocol version 2.1, the initial study sample size was calculated for both populations. We expected that 60% of our patients would be imaged for recurrent disease after surgery and/or radiation therapy, and we expected that 40% of our patients would be imaged prior to initial therapy for glial malignancy.

Population 1: Initially, the study's primary endpoint was misclassification rate as our statistical endpoint, defined as the percentage of patients that are classified incorrectly as either recurrent disease and treatment related changes (ie misclassification rate = $[FP+FN]/[FP+FN+TP+TN]$).

True positive (TP): FET PET read as positive for tumor, pathology/follow-up demonstrates tumor recurrence in at least one biopsy sample.

False positive (FP): FET PET read as positive for tumor, pathology/follow-up negative tumor recurrence in none of the biopsy samples.

True negative (TN): FET PET read as negative for tumor, pathology/follow-up negative tumor recurrence in none of the biopsy samples.

False negative (FN): FET PET read as negative for tumor, pathology/follow-up demonstrates tumor recurrence in at least one biopsy sample.

The sample size was calculated based on three subpopulations:

1. **Recurrent metastatic disease:** We estimated that there would be a prevalence of 65% for recurrent metastatic tumor at time of imaging. Papers that estimate misclassification rate have shown a misclassification rate of 24% (sensitivity of 86.7%, specificity of 68.2%, and a prevalence of 43%) for perfusion MRI (9), a misclassification rate of 46% (sensitivity of 59%, specificity of 41%, and a prevalence of 75%) for lesion quotient MRI. For FET PET, the literature has shown a misclassification rate ranging from 7 to 17%:
 - Misclassification rate of 17% with a sensitivity of 83%, specificity of 85% and prevalence of 84% (10).
 - Misclassification rate of 7% with a sensitivity of 95%, specificity of 91% and prevalence of 48% (11).

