9.2.2 Analysis of Primary Endpoints

Sensitivity, specificity, and 95% confidence interval (CI) will be calculated per the formulas in [Section 8.2.2](#), using the definitions of TP, FP, TN, and FN from [Section 8.1.3](#) and the CSOT. This will be done on a subject-specific basis based on the blinded readers' overall assessment.

The lower boundary of the 95% confidence interval for sensitivity will be compared to the threshold of 0.70 and for specificity it will be compared to 0.68.

Overall study success criteria: the lower bounds of the 95% CIs of the primary analysis of sensitivity and specificity must be greater than or equal to 0.70 and 0.68 respectively for at least the same 2 out of 3.

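### Section 8.1.3.1 defines a false negative as the same cell as a true negative, so a missed recurrence has no stated definition in the text that the co-primary analysis cites

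*Combined protocol and SAP*

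**What the plan says.** Section 8.1.3.1 sorts each lesion into one of four categories. TP is a positive read that the truth bears out. The other category for a positive read is worded "False positive (FP): FET PET read as positive for progression/recurrence, standard of truth does not confirm progression/recurrence". Two categories remain for a negative read. One of them pairs it with a negative truth: "True negative (TN): FET PET read as negative for progression/recurrence, standard of truth confirms negative for progression/recurrence". The last bullet in the set of four, and the one at issue here, says "False negative (FN): FET PET read as negative for progression/recurrence, standard of truth does not confirm progression/recurrence".

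Section 8.1.2.1 makes the truth binary: "The CSOT of progression/recurrence (positive) or TRC (negative) will be determined for each individual lesion and for each subject overall".

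Section 8.1.3.2 builds each reader's subject-level result from the lesion labels, in the order TP, FP, FN, TN, missing. Section 9.2.2 points back to section 8.1.3 for its categories: the co-primary endpoints follow the section 8.2.2 formulas, with the counts obtained "using the definitions of TP, FP, TN, and FN from" there. Section 9.2.3 does the same for the secondary accuracy endpoints.

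Section 8.2.2 gives sensitivity as TP/(TP+FN). In words, it is the share of true-positive scans among patients with a positive standard of truth.

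**The concern.** The FN bullet ends with the same clause as the FP bullet. In the FP bullet that clause can only mean truth-negative. Read the same way in the FN bullet, it makes FN a PET-negative, truth-negative lesion, which is what TN already covers. The remaining cell, PET negative with truth positive, is the one that a false negative should describe, and no bullet describes it.

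FN sits in the denominators of sensitivity and NPV and enters accuracy and the misclassification rate. Two neighbouring rules also rely on it:

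- For a lesion recorded by only one of the two evaluations, "the non-recorded evaluation will be assessed as negative for determination of the lesion-specific result (TP, FP, TN, or FN"). A recurrence that the Truth Panel records and a reader does not therefore becomes PET negative, truth positive, which is the undefined cell.
- The subject-level hierarchy has no place for a lesion without a label. If such a lesion were treated as missing (an assumption, since the plan does not say), a subject with one missed recurrence and one TN lesion would be scored TN.

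At stake is whether the text cited for a co-primary endpoint, in a study meant to support an NDA (section 1.1), fixes how that endpoint is counted.

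**Working it through.** **Logic.** PET is read as positive or negative and truth is positive or negative, which gives four cells.

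| PET | Truth | Label under the written bullets |
|---|---|---|
| positive | positive | TP |
| positive | negative | FP |
| negative | negative | TN and FN |
| negative | positive | none |

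**Inputs (section 9.1.1).** N = 118, prevalence of recurrence 0.50, sensitivity 0.81, specificity 0.79. N is taken as given and used only to size the table. I assume one result per subject, so that lesion and subject labels coincide.

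**Expected cells.** Truth-positive: 118 × 0.50 = 59. Truth-negative: 118 − 59 = 59.

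- Detected recurrences: 0.81 × 59 = 47.79
- Missed recurrences: 0.19 × 59 = 11.21
- Correct negatives: 0.79 × 59 = 46.61
- False positives: 0.21 × 59 = 12.39

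**Step 1: the plan's own values, with FN as PET negative and truth positive.**

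- Sensitivity = 47.79/(47.79 + 11.21) = 47.79/59 = 81.0%
- Specificity = 46.61/(46.61 + 12.39) = 46.61/59 = 79.0%
- NPV = 46.61/(46.61 + 11.21) = 46.61/57.82 = 80.6%

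This returns the assumed sensitivity and specificity.

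**Step 2: literal wording, shared cell called TN.** FN is empty and the 11.21 missed recurrences drop out.

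- Sensitivity = 47.79/47.79 = 100%, however many recurrences are missed
- Specificity = 79.0%, unchanged
- NPV = 46.61/46.61 = 100%

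**Step 3: literal wording, shared cell called FN.** TN is empty and the missed recurrences again drop out.

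- Sensitivity = 47.79/(47.79 + 46.61) = 47.79/94.40 = 50.6%
- Specificity = 0/(0 + 12.39) = 0%

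This "sensitivity" would also move with prevalence and specificity, which a true sensitivity does not.

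**Step 4: against the success threshold.** Rounding the cells to 48, 11, 47 and 12, the lower 95% Wilson limits for sensitivity in one reader are:

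| Reading | Sensitivity | Lower limit | Threshold (section 9.2.2) |
|---|---|---|---|
| Intended FN | 48/59 = 81.4% | 0.696 | 0.70 |
| Shared cell called TN | 48/48 = 100% | 0.926 | 0.70 |
| Shared cell called FN | 48/95 = 50.5% | 0.406 | 0.70 |

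On this table the three readings fall just below, well above and far below the threshold.

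**The case against.** The strongest reply is that the current text already settles what FN must mean.

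- Section 8.2.2 sets sensitivity against patients with a positive standard of truth, so TP + FN has to equal all truth-positive patients. It also describes misclassification as an incorrect scan result, which a correct negative is not.
- Section 9.2.2 cites the section 8.2.2 formulas together with the section 8.1.3 definitions.
- Section 8.1.3.1 requires every lesion to receive one of the four labels. With TP, FP and TN correctly defined, one cell and one label remain.
- Section 8.1.3.2 ranks FN apart from TN and gives an example with a TP lesion and an FN lesion.
- The superseded calculation in section 9.1.2 has the conventional meaning: "False negative (FN): FET PET read as negative for tumor, pathology/follow-up demonstrates tumor recurrence in at least one biopsy sample".

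All of this stands. The repeated ending looks like a copying slip from the FP bullet, and a careful statistician would probably count correctly. An output with no false negatives at all, or with a specificity of zero, would also be noticed on checking.

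A reader might infer that sensitivity cannot be computed correctly under this plan, or that the co-primary result will be meaningless. The documents do not support that, because section 8.2.2 gives a usable definition and nothing shows that any analysis was programmed to the faulty bullet.

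The reply does not remove the contradiction. Section 9.2.2 cites both the section 8.2.2 formulas and the section 8.1.3 definitions, the two disagree on FN, and no rule says which governs. Counting correctly means setting aside a definition that the primary analysis expressly cites.

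**Conclusion.** Wrong as written. The FN bullet in section 8.1.3.1 duplicates TN, leaves the missed recurrence without a stated definition, and conflicts with the verbal definition of sensitivity in section 8.2.2. The text is operative for the co-primary and the secondary accuracy endpoints.

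Under the plan's own assumptions, a literal reading gives a sensitivity of 100% or about 51%, against the intended 81%. Those two figures rest on a 59/59 split, one result per subject, and a program that overrides section 8.2.2. They show how far the wording departs from the intent and do not predict a result. A reader might also take the Wilson limits to mean that the slip would change the trial's outcome. They come from a single illustrative table for one reader, whereas the success rule needs both endpoints to pass for the same two of three readers.

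The logical fault itself depends on none of these numbers. It says nothing about whether 118 subjects are enough, which is a separate question.

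**What to change.** Replace the second half of the FN bullet in section 8.1.3.1 so that FN means a FET PET read negative for progression or recurrence where the standard of truth confirms progression or recurrence. The four categories are then mutually exclusive and cover every case. They agree with section 8.2.2, and the rule for lesions recorded by only one evaluation and the subject-level hierarchy work as they stand.

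The cost is one sentence. Under section 10.4 it needs a documented amendment, signed by the investigator and approved by the PRC and the CHR before implementation. It changes no data collection, sample size or patient procedure. Any analysis program already drafted should be checked to confirm that it counts PET-negative, truth-positive results as FN.
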